8.4. Total Blood Volume Required for Study

Table 8-1 Approximate Blood Volume per Subject

Test	Number of Samples	Volume (mL)	Total (mL)
Serology (serum)	1	5	5
Hematology (blood)	4	3	12
Chemistry (serum)	4	7	28
Biomarker (serum)	4	7	28
Pharmacogenomics sample (blood)	1	7	7
Total	14	--	80

8.5. Data Quality Assurance

This clinical trial will be monitored according to current Ardelyx Standard Operating Procedures (SOP) or its CRO designee’s SOP. Steps to be taken to assure the accuracy and reliability of data include the selection of qualified Investigators and appropriate study sites, review of protocol procedures and the administration of informed consent with the Investigator and associated site personnel prior to study start, and periodic monitoring visits by Ardelyx personnel or its CRO designee. During the trial, the Investigator shall permit Ardelyx or its CRO designee to verify the progress of the trial on site as frequently as necessary. Qualified personnel will review case report form data for accuracy and completeness against source documents during on-site monitoring. Data discrepancies will be resolved with the Investigator or designees, as appropriate. The

Investigator shall make the eCRFs and source documents available, provide missing or corrected data and sign the eCRFs. No personal information will be recorded on the eCRFs in accordance with HIPAA regulations.

An independent Quality Assurance (QA) department, Ardelyx designees and/or regulatory authorities may review this trial. This implies that auditors/inspectors will have the right to inspect the trial center(s) at any time during and/or after completion of the trial and will have access to source documents, including the subject's file. By participating in this trial, Investigators agree to this requirement. Measures will be undertaken to protect subject data handed over by the Investigator to Ardelyx and to inspectors against disclosure to unauthorized third parties and subject confidentiality will be maintained at all times.

9. ADVERSE EVENTS

9.1. Adverse Event

An **adverse event** (AE) is any untoward medical occurrence in a subject administered a pharmaceutical product, whether or not the occurrence has causal relationship with this treatment. An adverse event can therefore be any unfavorable and unintended sign (including an abnormal laboratory finding), symptom, or disease temporally associated with the use of an investigational product, whether or not considered related to the investigational product. This includes any newly occurring event or previous condition that has increased in severity or frequency since the administration of the investigational product.

Worsening of IBS symptoms is not considered an adverse event unless the frequency and/or severity of the symptom(s) are outside of what the subject considers normal for their IBS.

9.2. Severity

The term “severe” is used to describe the intensity (severity) of a specific event (as in mild, moderate, or severe myocardial infarction). Even though the event itself may be of relatively minor medical significance (such as a severe headache), this is not the same as “serious,” which is based on subject/event outcome or action criteria as described above and are usually associated with events that pose a threat to a subject’s life or functioning. A severe adverse event is not necessarily serious. For example, persistent nausea of several hours duration may be considered severe nausea but not meet the definition of a SAE. On the other hand, a stroke resulting in only a minor degree of persistent disability may be considered mild, but would be defined as a SAE based on the above noted criteria. Seriousness (not severity) serves as a guide for defining regulatory reporting obligations.

For both serious and non-serious adverse events, the Investigator must determine the severity of the event using the following definitions:

Mild The event does not interfere in a significant manner with the subject’s normal functioning level. It may be an annoyance but does not cause any limitation in usual activity.

Moderate The event produces some impairment of functioning but is not hazardous to health. It is uncomfortable or an embarrassment and may cause some limitation in usual activity.

Severe The event produces significant impairment or incapacitation and is a definite hazard to the subject’s health.

9.3. Unexpected Adverse Drug Experience

An unexpected adverse experience is any adverse drug experience, the specificity or severity of which is not consistent with the current Investigator’s Brochure, or if an Investigator’s Brochure is not required or available, which is not consistent with the risk information described in the general investigational plan or elsewhere in the current application, as amended. “Unexpected,” as used in this definition refers to an

adverse drug experience that has not previously been observed (e.g., included in the Investigator's Brochure) rather than from the perspective of such an experience not being anticipated from the pharmacological properties of the pharmaceutical product.

9.4. Causality

Association of adverse events to the study drug will be made using the following definitions:

Not related: The event is most likely produced by other factors such as the subject's clinical condition, intercurrent illness, or concomitant drugs, and does not follow a known response pattern to the study drug, or the temporal relationship of the event to study drug administration makes a causal relationship unlikely

Possibly-related: The event follows a reasonable temporal sequence from the time of drug administration, and/or follows a known response pattern to the study drug, but could have been produced by other factors such as the subject's clinical condition, intercurrent illness, or concomitant drugs

Probably-related: The event follows a reasonable temporal sequence from the time of drug administration, and/or follows a known response pattern to the study drug, and cannot be reasonably explained by other factors such as the subject's clinical condition, intercurrent illness, or concomitant drugs.

9.5. Serious Adverse Event

A **serious adverse event (SAE)** is any untoward medical occurrence, that at any dose, regardless of causality:

- results in death.
- is life-threatening. Life threatening means that the subject was at immediate risk of death from the reaction as it occurred, i.e., it does not include a reaction that, had it occurred in a more severe form might have caused death.
- requires in-patient hospitalization or prolongation of existing hospitalization. Hospitalization admissions and/or surgical operations scheduled to occur during the study period, but planned prior to study entry are not considered AEs if the illness or disease existed before the subject was enrolled in the trial, provided that it did not deteriorate in an unexpected manner during the trial (e.g., surgery performed earlier than planned).
- results in persistent or significant disability/incapacity. Disability is defined as a substantial disruption of a persons' ability to conduct normal life functions.
- is a congenital anomaly/birth defect.
- An important medical event that may not result in death, be life-threatening, or require hospitalization but may be considered a SAE when, based upon appropriate medical judgment, it may jeopardize the subject

and may require medical or surgical intervention to prevent one of the outcomes listed in the definition of SAE. Examples of such medical events include allergic bronchospasm requiring intensive treatment in an emergency room or at home, blood dyscrasias or convulsions that do not result in in-patient hospitalization, or the development of drug dependency or drug abuse.

9.6. Procedures for Recording and Reporting AEs and SAEs

Adverse events, both serious and non-serious, will be reported between Day 1 (Randomization) and the final visit (up to Day 183, Visit 9). Medical events that occur between the signing of the informed consent and the first dose of study drug will be documented as part of the subject's medical history and recorded on the appropriate eCRF page.

All adverse events spontaneously reported by the subject and/or in response to an open question from study personnel or revealed by observation, physical examination or other diagnostic procedures will be recorded on the appropriate page of the eCRF. Any clinically relevant deterioration in laboratory tests or other clinical finding is considered an adverse event and must be recorded on the appropriate pages of the eCRF. When possible, signs and symptoms indicating a common underlying pathology should be noted as one comprehensive event or diagnosis.

All serious adverse events occurring during the course of the study must be reported by email, or fax immediately to:

In no event shall a SAE be reported more than twenty-four (24) hours after the Investigator becomes aware of such event. The report of an SAE by the Investigator must provide the following minimal information: protocol number, subject number, subject's initials and date of birth, nature of the adverse event and attributes such as the severity of the event and causality. Events will be considered suspected adverse drug reactions if classified by the Investigator as possibly-related or probably-related.

A report of a SAE by telephone must always be confirmed by a written, more detailed report within 24 hours of the Investigator becoming aware of the event. The SAE Reporting Forms are provided to each clinical study site in the Study Manual. The Investigator should provide the following documentation at the time of notification, if available:

- SAE Reporting Form
- Concomitant and support medication pages;
- Relevant diagnostic reports;
- Relevant laboratory reports;
- Admission notes; if applicable

Hospital discharge summary; if applicable

Ardelyx will assume responsibility for appropriate reporting of adverse events to regulatory authorities. Ardelyx will report Suspected Unexpected Serious Adverse Reactions (SUSARs) to all investigational sites.

It is the responsibility of the Investigator to promptly notify the Institutional Review Board (IRB)/Independent Ethics Committee (IEC) of all SAEs, as well as any unanticipated problems that involve significant risk to subjects. A copy of the IRB/IEC notification should be placed in the sites' regulatory binder.

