16.1 Study Information

16.1.1 Protocol and protocol amendments

The following document is included:

- [Final protocol, dated 06 Oct 2015](#)

CLINICAL STUDY PROTOCOL

Protocol No. TEN-01-302

A 26-Week, Randomized, Double-Blind, Placebo-Controlled Study to Evaluate the Efficacy and Safety of Tenapanor for the Treatment of Constipation-Predominant Irritable Bowel Syndrome (IBS-C)

6 October 2015
Edition No. 1

SPONSOR:

Ardelyx, Inc.
[name]
[name]

Confidentiality Statement

This document and the information contained herein or attached hereto ("Confidential Material") are confidential and proprietary to Ardelyx, Inc. This Confidential Material should be viewed only by those individuals or companies that have been given prior authorization to do so by Ardelyx, Inc. ("Authorized Users"). This Confidential Material should not be made available in any form to any person or company, other than the Authorized Users and their respective employees or associates on a need-to-know basis, without the prior written consent from Ardelyx, Inc.

PROTOCOL SUMMARY

Study Title	A 26-Week, Randomized, Double-Blind, Placebo-Controlled Study to Evaluate the Efficacy and Safety of Tenapanor for the Treatment of Constipation-Predominant Irritable Bowel Syndrome (IBS-C)
Sponsor	Ardelyx, Inc.
Study Phase	3
Treatment Groups	2 treatment groups; ~600 subjects total; ~300/group with a ratio of 1:1 Tenapanor:placebo
No. of Sites	100-120
Dose Form and Frequency	Tablet(s), placebo matched Twice daily (BID)
Doses	Placebo, and tenapanor 50 mg BID (total daily doses; placebo, and 100 mg)
Methodology	This is a 26-week, multi-center, randomized, double-blind, placebo controlled study to evaluate tenapanor 50 mg BID in subjects with IBS-C (Rome III criteria). A 2:1 screen to randomization ratio is expected.
Duration	For each subject, the entire study will last for a total of 28 weeks; including 26 weeks of treatment, preceded by a 2 week screening period.

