8.1.1 Evaluations and procedures at Visit 1 (Day -14)

The procedures outlined for Visit 1 must be completed prior to enrolling the subject into the study. The following procedures will be conducted at Visit 1:

- Informed Consent (must be signed prior to discontinuing any prohibited medications or prior to the conduct of any study-related procedure)
- Inclusion/Exclusion Criteria
- Demographics
- Medical History, including IBS-C and other GI history
- Prior and Concurrent Medications
- Physical Exam
- Vital Signs
- Height
- Serum Chemistry and Hematology
- Biomarker sample
- FSH Test, as appropriate
- Serology
- Urine Pregnancy Test
- Urinalysis
- ECG
- Subjects will be instructed on the use of the telephone diary and begin

calling into the diary the evening of Visit 1 (Day -14)

- Subjects will be instructed to discontinue the use of all prohibited medications as outlined in [Section 5.6](#).

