8.3.1.1 Adverse events

Monitoring of treatment emergent adverse events will be conducted throughout the study beginning on Day 1 (Randomization). Adverse events, including serious adverse events will be recorded in the eCRFs through the end of the study. All adverse events should be followed by the investigator until they are resolved or are clearly determined to be due to a subject's stable or chronic condition or concurrent illness(es). Definitions, documentation, and reporting of adverse events are described in detail in [Section 9](#).

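### Serious events between consent and first dose have no clear 24-hour reporting route to the sponsor

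*Protocol*

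**What the plan says.** Protocol Section 9.6 opens with a reporting window: "Adverse events, both serious and non-serious, will be reported between Day 1 (Randomization) and the final visit", which is Visit 9. It then deals with the time before dosing: "Medical events that occur between the signing of the informed consent and the first dose of study drug will be documented as part of" the medical history, entered on the eCRF. No exception is made for serious events.

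The same section also carries a general duty: "All serious adverse events occurring during the course of the study must be reported by email, or fax immediately to" a contact whose details were removed from the public copy. A limit of 24 hours from the investigator's awareness follows. The Duration row of the Protocol Summary says that "the entire study will last for a total of 28 weeks; including 26 weeks of treatment, preceded by a 2 week screening period".

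The definitions refer to dosing. Section 9.1 defines an adverse event as "any untoward medical occurrence in a subject administered a pharmaceutical product"; Section 9.5 says that a serious adverse event "is any untoward medical occurrence, that at any dose, regardless of causality", meets one of the listed outcomes. Section 8.3.1.1 states: "Monitoring of treatment emergent adverse events will be conducted throughout the study beginning on Day 1 (Randomization").

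The protocol acts on subjects before Day 1. Section 4 has them stop all prohibited medications at Visit 1 (Day -14), and Section 8.1.1 says that consent "must be signed prior to discontinuing any prohibited medications or prior to the conduct of any study-related procedure". Section 5.5 permits bisacodyl during screening, for at most two uses.

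**The concern.** Screening is not passive observation here. The protocol tells consented subjects to stop drugs that they may be taking, and lets them use a stimulant laxative. If one of these requirements, or a screening procedure, leads to a hospitalisation, the sponsor needs to hear quickly, because other subjects are going through the same step. A site that follows the Day 1 window and the medical-history rule would file the event as history and start no 24-hour clock. A site that follows the general sentence would report it. The same event could be handled in two ways.

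What is at stake is prompt notice to the sponsor. The record of the event is not lost, and no efficacy result or randomised comparison is affected.

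**Working it through.** The plan states no figure on this point, so the check sets the provisions side by side. Arithmetic gives context only.

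**Provisions that point to exclusion of screening events**

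1. Section 9.6, first rule: reporting of both serious and non-serious events starts on Day 1.
2. Section 9.6, second rule: events from consent to first dose go to medical history, with no carve-out for serious ones.
3. Section 7: the adverse event row of the schedule starts at Visit 3. The Visit 1 and Visit 2 lists (Sections 8.1.1 and 8.2.1) have no adverse event item.
4. Sections 9.1 and 9.5: the definitions refer to an administered product and to dose.
5. Section 9.4: the causality categories address the study drug only, so none identifies drug withdrawal or rescue as the cause.

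**Provisions that point to inclusion**

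1. Section 9.6, general sentence: all SAEs during the study are reported immediately, within 24 hours.
2. Protocol Summary: the study is 28 weeks, screening included.

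**Which prevails.** No text gives the general sentence priority over the specific Day 1 start. The first two rules also collide on Day 1 itself. Reporting starts at randomisation, but medical-history filing runs to the first dose, which Section 6.3 places just before dinner that day. A serious event in those hours falls under both rules.

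**Other routes**

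- Sections 9.6 and 9.7 send unanticipated problems with significant risk promptly to the IRB/IEC. No sponsor deadline is attached.
- Section 11.7 asks for eCRF entry for every screened subject, preferably the same day. That preserves the data but is not expedited notice.
- Section 9.7 gives a 48-hour sponsor deadline for drug-related SAEs after study completion. The pre-dose period has no explicit counterpart.

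**Size of the window**

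- Share of study time before the reporting window, per randomised subject: 2 / 28 weeks = 14 / 196 days = 7.1%. It is more if consent precedes Visit 1, which footnote a of the schedule allows.
- Implied number screened (2:1 ratio, 600 randomised): 600 × 2 = 1,200.
- Never randomised: 1,200 − 600 = 600, and 600 / 1,200 = 50%. This is an upper figure, since some may fail telephone pre-screening before consent.
- Person-time, assuming a full 14 days each: 600 × 14 / 365.25 = 23 person-years for randomised subjects; 1,200 × 14 / 365.25 = 46 if every screened subject completes screening. Early screen failures lower the second figure.

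These figures measure time and headcount, not events. The documents do not say how many subjects stop a drug or use rescue during screening, so no event count can be derived.

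**The case against.** The strongest answer is that a 24-hour route already exists on a plain reading: all SAEs during the study must be reported, and the study is described as including screening. This is a real alternative reading. It makes the route ambiguous but does not settle the matter, because the specific Day 1 start in the same section expressly names serious events.

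Several lesser points stand in part:

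- Section 8.3.1.1 ties its Day 1 start to treatment-emergent events, which mostly arise after dosing, so it is weak support. The explicit Day 1 start for SAEs rests mainly on one sentence in Section 9.6.
- Bisacodyl is itself a pharmaceutical product, so the definitions do not clearly exclude a serious event after rescue use.
- The treatment-emergent definitions (Protocol Section 10.7.7, SAP Section 3.8.1) allow for some events that start before dosing. They set no reporting clock.
- Exposure is limited. Exclusions 5 to 7 remove many subjects who would have to stop a drug, stable antidepressants, antipsychotics and iron may continue, rescue is capped, and subjects are told to contact the investigator before using it.
- The Study Manual and the reporting contact block are not available, and either might state when reporting starts. The protocol should not depend on them for this.

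It is also fair to say that nothing in the documents requires SAE reporting from consent. The recommendation is a design preference, though a cheap one.

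**Conclusion.** The concern holds as a minor safety-reporting point. Section 9.6 gives no clear 24-hour route to the sponsor for a serious event between consent and first dose, although protocol requirements could cause one. To say that no route exists at all would go too far. The conclusion rests on the protocol text alone and assumes that no unseen site document resolves the conflict. The number of events affected cannot be estimated and is likely very small.

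**What to change.** In Section 9.6, with matching words in Section 8.3.1.1, require SAE reporting to the sponsor within 24 hours from informed consent for all screened subjects. At a minimum, cover serious events related to study procedures, protocol-required medication withdrawal or rescue use. State that this start point governs the general 24-hour sentence, and limit the medical-history rule to non-serious events. Non-serious adverse event collection can still begin at first dose.

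The change is to protocol wording only and uses the existing SAE form and reporting address. The cost is a few additional SAE reports, some from subjects who are never randomised.

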9.7. Monitoring of Adverse Events and Period of Observation

Adverse events, both serious and non-serious, will be recorded on the eCRFs up to and including the final visit (Day 183, Visit 9). All adverse events should be monitored until they are resolved or are clearly determined to be due to a subject's stable or chronic condition or concurrent illness(es).

Follow-up data concerning the SAE (e.g., diagnostic test reports, physician's summaries, etc.) must also be submitted to the Sponsor as they become available, preferably by facsimile. All serious adverse events, as well as any unanticipated problems that involve significant risk to subjects, must be promptly reported by the Investigator to his/her Institutional Review Board (IRB). Should the FDA or other pertinent regulatory authorities require that Ardelyx submit additional data on the event, the Investigator will be asked to provide those data to Ardelyx in a timely fashion.

The Investigator will review each serious adverse event report and further evaluate the relationship of the adverse event to the study drug and to the subject's underlying disease. Based on the Investigator assessment of the adverse event, a decision will be made concerning the need for further action. The primary consideration governing further action is whether new findings affect the safety of other subjects participating in the clinical study. If the discovery of a serious and unexpected adverse event related to the study drug raises concern over the safety of its continued administration to subjects, the Sponsor will take immediate steps to notify the FDA and other pertinent regulatory authorities and all Investigators participating in clinical studies of the study drug.

Any serious adverse event that occurs at any time after completion of the study, which the Investigator considers to be related to study drug, must be reported to Ardelyx within forty-eight (48) hours of the Investigator becoming aware of the event.

9.8. Pregnancy

Pregnancy by definition is not considered to be a serious adverse event unless the pregnancy or the outcome meets the criteria in [Section 9.5](#). However, pregnancy in subjects that have received the study drug must be followed to assess congenital anomalies.

